## **Study Design**

This study will be a prospective, non-randomized, open-label study of Omegaven™ with a total enrollment of 100 patients, for provision of parenteral lipid calories. The study cohort, receiving the PN at 1g/kg/day, will be compared to historical controls at UNMC where parenteral lipid calories were provided exclusively through soybean-based formulations, as well as, assessing the study cohorts need for small bowel and liver transplantation.

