#### **4. Treatment/Follow-up Period**

During the follow-up period, patients will continue to be followed by the Intestinal Rehabilitation Program per our standard care for any patient on PN: All patients in IRP are followed with regular blood work, including CBC/diff and CMP at least weekly initially, and in most cases 2-3 times per week. Based on clinical progress, the frequency of laboratory evaluation may be reduced, but is rarely less than once weekly until patients are stable and off PN. These procedures and tests would continue to be performed.

In addition to standard nutritional monitoring, essential fatty acids and serum triglycerides levels will be sent monthly. If a patient should experience lipid intolerance, then serum lipid profiles, including triglycerides, will be sent weekly for the first 4 weeks of therapy, and if stable will be reduced to every two weeks. This monitoring is additional to what would be standard in this population. Any adverse experiences will be recorded for every patient throughout the entire enrollment of the study.

Patients will remain on Omegaven™ until weaned from PN and may continue monotherapy with Omegaven™ as an additional source of calories after the dextrose/protein portion of PN is discontinued.

Upon returning home, patients will be returned to the care of the physician who referred them for participation in the study. Arrangements will be made with the patient's primary care physician to continue usual follow-up. Patients will initially be seen by their primary care physician within one week of returning home.

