### Treatment Period

- Vital Signs (daily)
- Signs and Symptoms, daily
- Daily TPN/PN intake
- Total 24-hour oral/enteral intake
- Total 24-hour urine and stool volumes

- Clinical Chemistries - (to include any or all or the following at the discretion of the investigator, 1 or more times per week based on the clinical status of the patient):
  - Blood urea nitrogen (BUN)
  - Creatinine
  - Electrolytes (sodium, potassium, chloride, bicarbonate, magnesium)
  - Calcium
  - Phosphorus
  - Serum amylase
  - Total Protein
  - Albumin
  - Triglycerides
  - Liver function (total bilirubin, direct and indirect bilirubin, alkaline phosphatase, SGOT, SGPT, LDH)

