### **Discontinuation of Therapy –**

- In the event that a patient is unable to achieve adequate calories parenterally and is unable to tolerate enteral feeds, it may be necessary to evaluate whether or not the patient should continue the study with Omegaven™ as monotherapy or resume therapy with conventional fat emulsions so that additional parenteral fat calories can be given.
- Adverse Event (AE) – Any patient with anaphylactic or allergic reactions to Omegaven™ will not continue treatment and will be withdrawn from the protocol.
- Inter-current Illness – If a patient develops an illness during the course of the study that is not associated with the condition under study and that requires treatment inconsistent with the protocol requirements (such as an interruption of regular participation in the study), the patient may be discontinued from further participation in the study. A patient may also be discontinued from the study if he develops an inter-current illness or complication that in any way justifies his withdrawal from the study. However, if an inter-current illness develops which can be managed without significant interference with the requirements of the protocol, the patient need not be discontinued.
- The patient will complete treatment with Omegaven™ in this study when he/she is completely off PN, develops a contraindication for further use, or the patient/family requests to be removed from the study.

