## Statistical Analysis

Data from the two sets of patient population will be pooled and compared (i.e., current protocol patients prescribed Omegaven™ PN compared to historical controls where parenteral lipid calories were provided exclusively through soybean-based formulations). Potential for effect in different patient populations will be minimized by matching patients enrolled in the Omegaven™ protocol to historical controls. Frequency matching will be utilized given the difficulty of paired matching in this patient population. Specific matching criteria will include gender, age, etiology of short bowel syndrome, and severity of liver disease (parenteral nutrition- associated liver disease).

Continuous data will be expressed as mean +/- SEM. A two-way repeated measure ANOVA will be used to compare differences in the two groups with respect to changes between the Evaluation assessment and the subsequent analyses performed at Treatment and Treatment/Follow-up Assessments. Incidence of adverse events in each treatment arm will be compared using Fisher's exact test. Univariate and multivariate analysis will be used to identify baseline factors that may influence outcome. A P-value <0.05 will be considered statistically significant.

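### The repeated-measures ANOVA, the only efficacy test named, does not fit irregular, outcome-dependent laboratory data, so it can analyse a selected subset and can misstate the error rate

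*Combined protocol and SAP*

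**What the plan says.** Statistical Analysis names the test as follows: "A two-way repeated measure ANOVA will be used to compare differences in the two groups with respect to changes between the Evaluation assessment" and those made in the Treatment and Treatment/Follow-up periods. It is the only named test that compares the groups on efficacy. The other two statements cover different ground: "Incidence of adverse events in each treatment arm will be compared using" Fisher's exact test, and "Univariate and multivariate analysis will be used to identify baseline factors that may influence outcome". The threshold is "A P-value <0.05 will be considered statistically significant". The section gives no visit times or windows, missing-data rule, analysis set, covariance structure or sphericity correction.

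The data arise as follows.

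- **Testing.** In the Treatment Period, the investigator chooses any or all of a list of chemistries, "1 or more times per week based on the clinical status of the patient". The Extended Outpatient Treatment Period sets a weekly rhythm, but the choice of tests is again discretionary. Under 4. Treatment/Follow-up Period, progress changes the schedule: "the frequency of laboratory evaluation may be reduced, but is rarely less than once weekly until patients are stable and off PN".
- **End of treatment.** Under Patient Discontinuation, "The patient will complete treatment with Omegaven™ in this study when he/she is completely off PN"; a contraindication or a family request also ends it. Section 3. Treatment lets the clinical team remove a patient who cannot get adequate calories.
- **After treatment.** The Discontinuation of Therapy section under Omegaven™ Dosages keeps patients under the program's follow-up until they have recovered.
- **Groups.** The study is an "open-label study of Omegaven™ with a total enrollment of 100 patients", compared with frequency-matched historical controls whose number is not stated.

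**The concern.** Classical two-way repeated-measures ANOVA works on a complete grid of patients by common times. A patient with a missing cell is normally lost from it, and the standard F test for group-by-time is valid only under sphericity. Serial bilirubin values that drift at different rates in different patients violate that assumption.

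Where values are missing because a patient recovered or failed, the patients left in the grid are a selected group. If the reasons for leaving differ between a prospective cohort and controls taken from records, the two remnants can differ even when the lipid has no effect. If the reasons are the same, a real effect can be diluted. The hypothesis, which concerns normalization of liver enzymes and bilirubin, depends on this test.

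**Working it through.** The documents give no dropout rate, variance, visit count or number of controls, so there is no figure of the plan's own to reproduce. Everything in steps 2 to 6 rests on assumptions.

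**1. Which variables have a Treatment value.** Efficacy and Safety Variables lists 33 body, nutritional and laboratory variables: 2 body measures + 6 vitamins + 5 minerals and trace elements + 3 serum proteins + 1 essential fatty acids + 2 (citrulline, D-lactic acid) + 5 electrolytes + 2 renal + 7 liver = 33. The Treatment Period list contains 18 of them: calcium, phosphorus, total protein, albumin, 5 electrolytes, 2 renal, 7 liver. So 33 - 18 = 15 are absent. Essential fatty acids are added monthly elsewhere, and weight is added for outpatients, leaving 15 - 2 = 13 with no scheduled Treatment value. These 13 have Evaluation and Follow-up values only, because Treatment/Follow-up Assessments repeats nutritional status.

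**2. Share of patients with a complete grid.** If a fraction h is lost per month, the share complete after m months is (1 - h)^m.

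| h (assumed) | 6 months | 12 months |
|---|---|---|
| 5% | 0.95^6 = 74% | 0.95^12 = 54% |
| 10% | 0.90^6 = 53% | 0.90^12 = 28% |

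**3. Sphericity alone, complete data, no true effect, nominal 5%.** The uncorrected group-by-time F test was simulated with serially correlated errors (AR(1), correlation 0.8) or patient-specific slopes. At three times, error is about 5-6%. At 6 to 12 times it is roughly 8-16%, the top value depending on the slope variance.

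**4. Exit that depends on the outcome.** The simulation had 4,000 runs, 100 per group (100 controls assumed) and 7 common times. Log bilirubin had random intercept SD 0.6, slope SD 0.8 over the period, and AR(1) residual SD 0.3 with correlation 0.6. Exit per visit was 2-3%, plus an extra risk after a fall (recovery) or rise (failure) of more than 0.4 from baseline. Only completers were analysed; there was no true effect. GG is the Greenhouse-Geisser correction.

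| Extra exit risk (after fall / after rise) | Complete, controls / treated | Error, uncorrected | Error, GG | False difference (log units) |
|---|---|---|---|---|
| No exit at all | 100% / 100% | 11.4% | 4.9% | 0.00 |
| Both groups 10% / 10% | 73% / 73% | 10.7% | 4.7% | 0.00 |
| Both groups 25% / 25% | 51% / 51% | 10.9% | 5.0% | 0.00 |
| Controls 15% / 25%, treated 25% / 15% | 56% / 56% | 35% | 22% | 0.18 |
| Controls 0% / 25%, treated 25% / 25% | 68% / 51% | 52% | 37% | 0.24 |
| Controls 10% / 30%, treated 30% / 10% | 57% / 57% | 80% | 66% | 0.35 |

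The false difference is treated minus control. It makes the treated look worse here because their recovering patients leave; the opposite pattern would reverse the sign. A separate check, comparing completers on simple change from baseline, gave 5.1% with equal exit, about 9% with a mild difference and about 79% with opposite exit.

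With a true effect of -0.40 and the same 25% / 25% rule in both groups, the completer estimate is -0.27, about two thirds of the truth, and GG power falls from 87% to 41%.

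**5. A two-point reading.** Using each patient's change from baseline to the last value, error is 4.6-5.2% when exit is equal and 6.3-7.2% when it differs. With the true effect of -0.40 and equal exit, the estimate is -0.28 and power is 80%, against 87% without exit.

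**6. The alternative.** In a separate null simulation (150 trials, 100 per group, 6 months, exit driven by the last observed bilirubin and opposite in the two groups), the complete-case analysis gave a bilirubin ratio of 0.81 and 42% false positives. A linear mixed model gave 0.99 and about 5%. With 150 trials, 42% carries ±1.96 × √(0.42 × 0.58 / 150) = ±8 points, so about 34-50%. Exit depended only on observed values, so this scenario meets the mixed model's assumption by construction.

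**The case against.** A reader might infer more than the documents support.

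- **That incomplete patients will be dropped.** Nothing says so; it is how the classical test usually runs. Efficacy and Safety Variables defines change to the end of follow-up or of treatment, which allows a two-point reading with error close to 5%. This stands. But Statistical Analysis refers to both Treatment and Treatment/Follow-up assessments, and the plan does not choose between readings.
- **That stopping treatment means losing the patient's data.** It does not by itself: follow-up continues after Omegaven™ stops, and Duration of Therapy says only that participation does not bar a transplant, not that transplanted patients leave. This stands, so the completeness shares in step 2 are not predictions. That follow-up, however, has no fixed assessment times, ends at recovery and does not govern controls' existing records.
- **That the error rate is 8-16%.** This needs 6 to 12 visits, which the plan never states. At the three kinds of assessment it names, error is about 5-6%, and a routine correction handles the rest when exit is equal.
- **That 42% or 80% false positives should be expected.** Those figures need opposite exit patterns in the two groups, which no section describes. Unequal exit is plausible with historical controls but is not quantified.
- **That liver tests are too sparse.** Blood work is rarely less than weekly until patients are stable and off PN, so a monthly window would usually hold a value. This stands.
- **That 13 variables are never measured again.** They are repeated at follow-up, and globulin can be derived from total protein and albumin.

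**Conclusion.** The concern holds as a risk, not as a certain consequence. The only named efficacy test assumes a data structure that the plan does not produce, and no rule closes the gap. For the continuous laboratory and nutritional outcomes, it can analyse a selected subset and can misstate the error rate.

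The size depends on choices left open. It is small for a two-point change or for three assessments. With equal exit, the harm from a corrected completer analysis is a diluted effect and lost power, not false positives. Error becomes serious only when exit differs between groups (about 9% to 80%, by scenario), and a sphericity correction does not repair that: error was still 22-66% in the three scenarios of step 4. All of this assumes 100 controls and the stated variances and exit rates.

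A reader might also infer that the primary result is invalid for this reason. It is not affected: need for small bowel transplantation is an event outcome to which this ANOVA does not apply, and no test is named for it. Because the defect touches secondary outcomes and its effect is conditional, it should be fixed but is not disabling.

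**What to change.** In Statistical Analysis, replace the ANOVA with a linear mixed model that uses every available value in stated windows, for example weeks 4, 8, 12 and 24.

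- Include group, time, group-by-time and the variable's own baseline value.
- Use a covariance structure that does not assume sphericity (unstructured, or a patient random intercept and slope), with Kenward-Roger degrees of freedom.
- Name one week as the main contrast.
- Apply the same windows to the controls' records.
- For variables measured only at Evaluation and Follow-up, use ANCOVA on the baseline value.
- State how values after transplantation are used.
- Add one sensitivity analysis for values missing for reasons the observed data do not explain.

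The cost is SAP wording and a little programming, with no new data. The downside is reliance on a missing-at-random assumption, which is why the sensitivity analysis is needed. The change does not remove confounding from historical controls, and it does not supply a test for the primary objective, which needs its own analysis.

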### Efficacy and Safety Variables

The efficacy and safety variables in this study will be the change from the baseline assessment to the end of follow-up assessment or end of treatment assessment for the variables listed below. The variables will be determined from: the measurement of body weight, the recording of TPN prescriptions, blood and urine analyses, radiology reports, GI exams, and possible liver biopsies.

- Parenteral Nutrient Requirements (determined from the TPN/PN prescription)
  - TPN/PN infusions (days/week)
  - TPN/PN fluid volume (cc/week)
  - TPN calories (kcal/week)
  - TPN protein (g/week)
  - TPN lipid (g/week)
  - Intravenous vitamins (type and # of infusions/week)
  - Intravenous trace elements (type and # of infusions/week)
  
- Assessment of Nutritional Status
  - Body Composition
  - Body Weight
  
  - Nutrient and Metabolic Profile (Blood analyses)
  - Vitamins- A, B12, C, D, E, folate
  - Minerals and trace elements - calcium, phosphorus, iron, selenium, zinc
  - Serum Proteins - total protein, albumin, globulin
  - Lipid profile - essential fatty acids levels
  - Citrulline, D-lactic acid
  - Serum Electrolytes – (sodium, potassium, chloride, bicarbonate, magnesium)
  
- Assessment of Hydration Status/ Renal Function (Blood analyses)
  - Blood urea nitrogen
  - Serum creatinine

- Assessment of Liver Function (Blood analyses)  
Total bilirubin, direct and indirect bilirubin, alkaline phosphatase, SGOT, SGPT, LDH.
- Assessment of Upper and Lower GI tract/Liver  
Upper and Lower endoscopy, mucosal biopsies and bacterial cultures  
Ultrasound of abdomen/Small bowel follow through, Barium enema  
Liver biopsy (based on clinical indication)

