#### **Evaluation Assessments**

- Parenteral Nutrient Requirements (determined from the TPN/PN prescription)
  - TPN/PN infusions (days/week)
  - TPN/PN fluid volume (cc/week)
  - TPN calories (kcal/week)
  - TPN protein (g/week)
  - TPN lipid (g/week)
  - Intravenous vitamins (type and # of infusions/week)
  - Intravenous trace elements (type and # of infusions/week)

- Assessment of Nutritional Status
  - Body Composition
  - Body Weight
  - Nutrient and Metabolic Profile (Blood analyses)
  - Vitamins- A, B12, C, D, E, folate
  - Minerals and trace elements - calcium, phosphorus, iron, selenium, zinc
  - Serum Proteins - total protein, albumin, globulin
  - Lipid profile - essential fatty acids levels
  - Citrulline, D-lactic acid
  - Serum Electrolytes – (sodium, potassium, chloride, bicarbonate, magnesium)
- Assessment of Hydration Status/ Renal Function (Blood analyses)
  - Blood urea nitrogen
  - Serum creatinine
- Assessment of Liver Function (Blood analyses)
  - Total bilirubin, direct and indirect bilirubin, alkaline phosphatase, SGOT, SGPT, LDH.
- Assessment of Upper and Lower GI tract/Liver
  - Upper and Lower endoscopy, mucosal biopsies and bacterial cultures
  - Ultrasound of abdomen/Small bowel follow through, Barium enema
  - Liver biopsy (based on clinical indication)
- Vital Signs
- Baseline Signs and Symptoms
- Physical Examination
- Total 24-hour oral/enteral intake
- Total 24-hour urine and stool volumes

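### Continuous outcomes are compared on unadjusted change from Evaluation: precision is lost, and with non-randomised controls a baseline-adjusted result is needed beside it

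*Combined protocol and SAP*

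**What the plan says.** The analysis of continuous data is given in one sentence of the Statistical Analysis section: "A two-way repeated measure ANOVA will be used to compare differences in the two groups with respect to changes between the Evaluation assessment" and the assessments during treatment and follow-up. The section Efficacy and Safety Variables puts the outcomes on the same scale, as "change from the baseline assessment to the end of follow-up assessment or end of treatment assessment". Neither place names a baseline covariate.

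The starting values exist. The Evaluation Assessments list covers the PN prescription, the nutritional and renal measures, and the liver tests ("Total bilirubin, direct and indirect bilirubin, alkaline phosphatase, SGOT, SGPT, LDH").

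Comparability of the groups is left to the design. The Study Design section begins "This study will be a prospective, non-randomized, open-label study of Omegaven™ with a total enrollment of 100 patients", with historical controls from the same centre. On matching, the plan says "Frequency matching will be utilized given the difficulty of paired matching in this patient population", and then "Specific matching criteria will include gender, age, etiology of short bowel syndrome, and severity of liver disease". No measure or cut-point for severity is given.

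The one other use of baseline data is "Univariate and multivariate analysis will be used to identify baseline factors that may influence outcome". That describes a search for prognostic factors. It does not say that the comparison of Omegaven with control will be adjusted for them.

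**The concern.** Two things are at stake, and they differ in how firmly they can be stated.

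The first is precision. A change score subtracts the whole baseline value, whatever its correlation with follow-up. Adjustment subtracts only the part that predicts follow-up. When the groups start at similar levels, the change score is the noisier of the two for any correlation below 1.

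The second is bias. Without randomisation the groups may start at different levels. Frequency matching balances group totals on four factors. It does not fix the mean of each liver test, PN requirement or nutritional measure. If patients in both groups drift toward a common level, the group that starts higher falls further whatever lipid it receives, and the planned test counts that as a group difference. For the liver tests this is plausible. Omegaven patients enter on direct bilirubin at or above 2 mg/dl (Inclusion Criteria), which selects high values, and the Hypothesis section expects hepatic enzymes and bilirubin to return to normal, which is a common end point. How controls were selected, beyond the matching, is not stated.

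These variables carry the study hypothesis and the secondary objectives. The primary objective, need for small bowel transplantation, is not a change score.

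**Working it through.** The plan has no figure to reproduce. It gives an enrolment of 100 Omegaven patients and a significance level of 0.05, but no SD, correlation, effect size, power or number of controls. The inputs below are therefore assumptions: 100 per group, a two-sided test, correlation r between Evaluation and follow-up, and baseline gap d (Omegaven minus control). All quantities are in units of the outcome SD.

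**Which model is meant.** Changes may be analysed directly, or raw values may be analysed with Evaluation as one level of time. In the second case the group-by-time term is still a comparison of changes. Under either reading there is no adjustment for baseline.

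**Precision, one follow-up visit, d = 0.** The variance per patient is 2(1−r) for the change score and 1−r² for the adjusted analysis. The ratio is (1−r²)/[2(1−r)] = (1+r)/2.

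| r | change | adjusted | ratio |
|---|---|---|---|
| 0.3 | 1.40 | 0.91 | 0.65 |
| 0.5 | 1.00 | 0.75 | 0.75 |
| 0.7 | 0.60 | 0.51 | 0.85 |
| 0.9 | 0.20 | 0.19 | 0.95 |

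With two follow-up visits and equal correlations, the ratio runs from 0.53 (r = 0.3) to 0.93 (r = 0.9). As an example, at r = 0.5 and a true difference of 0.4 SD, power is 80.7% on change scores and 90.4% with adjustment. A baseline gap erodes the gain, because the adjusted variance becomes (1−r²)(1+d²/4) with equal groups. At r = 0.9 and d = 0.5 it is 0.202 against 0.200, a ratio of 1.01, so nothing is gained.

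**Bias, no true effect.** There are two explanations of a gap:

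- *Common mean.* Follow-up depends on baseline in the same way in both groups. The change difference is rd − d = −(1−r)d, and the adjusted difference is 0.
- *Stable gap.* The populations differ by d at both times. The change difference is 0, and the adjusted difference is d − rd = +(1−r)d.

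The error has the same size and the opposite sign. For d = 0.3, let B = (1−r)d. The standard errors are √[4(1−r)/100] for change and √[2(1−r²)(1+d²/4)/100] for the adjusted analysis. The false-positive rate is 1−Φ(1.96−B/SE)+Φ(−1.96−B/SE).

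| r | B | SE change | SE adjusted | change analysis, if common mean | adjusted analysis, if stable gap |
|---|---|---|---|---|---|
| 0.3 | 0.21 | 0.167 | 0.136 | 24% | 34% |
| 0.5 | 0.15 | 0.141 | 0.124 | 19% | 23% |
| 0.7 | 0.09 | 0.110 | 0.102 | 13% | 14% |

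In the case not shown for each method, its rate stays at about 5%.

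**Simulation check** (4,000 runs, r = 0.5, 100 per group):

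| gap | explanation | change | adjusted |
|---|---|---|---|
| 0.25 SD | common mean | 14.1% | 4.9% |
| 0.25 SD | stable gap | 4.3% | 17.1% |
| 0.5 SD | common mean | 41.2% | 4.5% |
| 0.5 SD | stable gap | 4.9% | 50.8% |

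The simulation agrees with the formulas. Neither method holds its error rate under both explanations.

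**The case against.** The strongest reply is that choosing between change scores and baseline adjustment in non-randomised groups is a long-standing dispute (Lord's paradox), and that the plan's choice is legitimate. If the historical and current patients differ stably, the planned analysis is unbiased and adjustment introduces the error, at somewhat higher false-positive rates than those that count against the plan. This stands. A reader might infer that baseline gaps necessarily leak into the treatment effect, or that the plan's error rate is inflated. The documents support neither inference, because they do not say how controls were selected beyond matching and so do not show which explanation applies. For the same reason they do not support replacing the planned analysis with an adjusted one.

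Three further replies stand in part. Matching on severity of liver disease should narrow gaps in the liver tests, and matching on age should narrow gaps in weight. But matching is at group level, severity is not defined, and no factor addresses PN requirements, vitamins or proteins. The univariate and multivariate analysis could be used to adjust the group effect, but the text does not commit to that. The bilirubin entry threshold makes regression to the mean plausible for liver tests, and does not by itself make it plausible for weight, vitamins or PN calories.

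None of this answers the loss of precision when baselines are similar.

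**Conclusion.** The concern holds in a limited form. For the continuous, mainly secondary, variables the plan relies on one unadjusted analysis of change. When baselines are similar, that costs precision: adjustment would remove 35% to 5% of the variance for r from 0.3 to 0.9 with one follow-up visit, and the gain disappears only when the correlation is very high and the gap is large. When baselines differ, the result depends on why they differ, which the plan leaves open. An error of (1−r) times the gap falls on the change analysis in one case and on the adjusted analysis in the other, so neither is safe alone.

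The actual size of any bias cannot be derived from the documents. Correlations, gaps, equal groups of 100 and two-sided testing are all assumed here. A reader might also extend the point to the trial's main conclusion, but the primary objective is need for small bowel transplantation, which this analysis does not touch.

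**What to change.** In the Statistical Analysis section:

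1. Pre-specify, for each continuous variable, a longitudinal model of the values after Evaluation. Its terms should be group, time, group-by-time, the variable's own Evaluation value, and the interaction of that value with time. Evaluation then enters as a covariate and not also as an outcome time point.
2. Keep the planned unadjusted comparison of changes and report the two results side by side.
3. Tabulate the baseline gap between groups for each variable. With one follow-up visit, the two estimates differ by (1 − fitted baseline slope) times the observed gap, so the table shows where they can diverge.
4. State in advance that a group effect counts as robust to the handling of baseline only where both analyses agree, and that any disagreement will be reported. Agreement settles this question only. It does not remove other differences between historical and current patients.
5. Say whether the multivariate analysis is meant to adjust the group effect.

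This changes wording only. Every patient who contributes a change already has the Evaluation value, so no new data are needed. The cost is one extra result per variable and the possibility of two answers that must both be shown.

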### **Duration of Therapy**

Patients will remain on Omegaven™ until weaned from PN and may continue monotherapy with Omegaven™ as an additional source of calories after the dextrose/protein portion of PN is discontinued.

In the event that a patient is listed for a liver or liver/intestinal transplant and an organ becomes available, the participation in this protocol will not preclude them from receiving the transplant.

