### **Discontinuation of Therapy**

Patients will continue to be followed by the UNMC Intestinal Rehabilitation Program upon discontinuation of therapy with Omegaven™ until they are completely free of any rehabilitation needs and are tolerating a full diet by mouth.

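### The adverse-event comparison with historical controls uses Fisher's exact test, which ignores observation time; cohort follow-up is open-ended, and no window, source or event definition is given for controls

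*Combined protocol and SAP*

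**What the plan says.** The Statistical Analysis section gives the adverse-event comparison one sentence: "Incidence of adverse events in each treatment arm will be compared using Fisher's exact test". The comparison is between Omegaven patients and historical controls at the same centre, and P<0.05 counts as significant.

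**Time at risk in the cohort.** The Treatment/Follow-up Period section says: "Any adverse experiences will be recorded for every patient throughout the entire enrollment of the study". Enrollment has no fixed length. Under Duration of Therapy, "Patients will remain on Omegaven™ until weaned from PN and may continue monotherapy with Omegaven™ as an additional source of calories". Under Patient Discontinuation, "The patient will complete treatment with Omegaven™ in this study when he/she is completely off PN, develops a contraindication for further use"; a request by the patient or family also ends treatment. After treatment, patients are followed "until they are completely free of any rehabilitation needs and are tolerating a full diet by mouth".

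**Controls.** No section gives their observation window, the records used to find their adverse events, or the event definitions applied.

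**Matching and adjustment.** "Specific matching criteria will include gender, age, etiology of short bowel syndrome, and severity of liver disease". For modelling, "Univariate and multivariate analysis will be used to identify baseline factors that may influence outcome". Follow-up time appears in neither.

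**Extra monitoring.** The Treatment/Follow-up Period section adds lipid tests beyond standard care: "essential fatty acids and serum triglycerides levels will be sent monthly", with weekly lipid profiles only after lipid intolerance. The Abstract and Monitoring and Possible Dose Reductions have triglycerides weekly. The Treatment Period and Extended Outpatient lists put them among chemistries chosen at the investigator's discretion.

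**The concern.** The chance that a patient has at least one event grows with the time observed and with how carefully events are looked for. The Side Effects section expects bloodstream infection and readmission in all short-bowel patients whatever the lipid, so these will accrue in both groups. A test on the proportion affected is a fair comparison only if observation time and recording are alike. The plan secures neither.

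If they differ, the P-value mixes the effect of the lipid with follow-up length and recording. Prospective recording could make Omegaven look worse than controls drawn from old records. Time at risk could go either way, because the rationale hopes both to allow more time for rehabilitation on PN and to bring PN to an end. A real excess of events could also be hidden. This is the only between-group test of adverse events in the plan; the change-from-baseline safety variables are analysed separately and are not at issue here.

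**Working it through.** The plan gives no event rate, control number, follow-up time or power for this comparison, so there is no figure of its own to reproduce. What follows is illustration.

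**Inputs.** From the documents: 100 treated patients, Fisher's test, P<0.05. Assumed: 100 controls, a two-sided test, constant event rates, complete follow-up, and 6 months in the group observed for less time.

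**Formula.** P(affected) = 1 − exp(−rate × years). The rejection probability is the sum of the binomial probabilities of all 2×2 tables with Fisher P<0.05.

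**1. Equal true rates, unequal time.** Example at 1 per year, 6 versus 12 months: 1 − exp(−0.5) = 0.393 against 1 − exp(−1) = 0.632; Fisher rejects 91% of the time although the rates are identical.

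| Rate per year | Equal time | 10% longer | 20% longer | 50% longer | Double |
|---|---|---|---|---|---|
| 0.1 | 2% | 2% | 3% | 6% | 17% |
| 0.5 | 3% | 4% | 7% | 26% | 71% |
| 1 | 4% | 5% | 11% | 44% | 91% |
| 2 | 3% | 6% | 13% | 56% | 96% |

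With equal time the test keeps its level. A 10% difference does little harm, and rare events are little affected until follow-up differs greatly.

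**2. Masking.** Take a true doubling, 2 against 1 per year.
- 6 months in both groups: 1 − exp(−1) = 0.632 against 1 − exp(−0.5) = 0.393; detected 91% of the time.
- 6 months at 2 per year against 12 months at 1 per year: 2 × 0.5 = 1 × 1, so both proportions are 0.632; detected 3% of the time.
- A log-rank test on time to first event detects it about 94% of the time in the same 6-versus-12-month setting (simulation).

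**3. Unequal recording, equal time.** With 40% truly affected in each group and controls' records capturing 80%, 70% or 50% of affected patients, control incidence becomes 32%, 28% or 20%, and Fisher rejects 17%, 37% or 84% of the time. A time-to-event method does not cure this: at 1 per year over 6 months, with the same shares of control events captured, log-rank rejects 16%, 31% or 76%.

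**4. Limit of the alternative.** Log-rank stays near 5% when censoring is unrelated to risk, but not otherwise. In a simulated 12-month window with half the patients at 0.5 and half at 1.5 per year, and early exits in one group only, it rejects 4.5% of the time if 40% leave regardless of risk. It rejects 16-18% if 80% of one risk class and none of the other leave.

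**The case against.** The strongest reply is that the documents show no imbalance. The controls come from the same centre, frequency matching on age, etiology and liver-disease severity may partly balance time on PN, the matching list is introduced with wording that does not close it, and routine blood work is standard for programme patients. At 10% longer follow-up the distortion is negligible. Adverse events are also not among the stated objectives.

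Much of this stands. It rules out any claim about size or direction and limits the weight of the point. It does not supply the missing elements: no follow-up criterion appears anywhere, the plan does not say that the controls were programme patients, and routine laboratory work does not settle how symptoms were found or how long controls were observed.

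A reader might also infer that no observation period is set for either group. That goes too far: cohort recording is tied to enrollment. It is patient-specific and open-ended, not absent; what is absent is any counterpart for controls.

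A further fair objection is that a fully adjusted Cox model would be unstable for rare events. At 0.1 per year over 6 months about 5 of 100 patients per group are affected (100 × 0.049), so adjustment must depend on event numbers.

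**Conclusion.** The point holds as a gap in the plan. Fisher's test on incidence is specified against historical controls without a common window, any handling of follow-up time, or a description of how control events are found. Following the plan as written can therefore give a wrong adverse-event conclusion in either direction.

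The consequence depends on quantities the documents do not give: from almost nothing at 10% longer follow-up to 17-96% false rejection when follow-up differs twofold, under the assumed rates and 100 versus 100. A reader might infer from the larger figures that the comparison is expected to fail, or that it is biased against Omegaven; the documents support neither.

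This should be corrected, but it does not bear on the primary objective, the need for small bowel transplantation, or on the stated secondary ones. The Abstract does hypothesise good tolerance, so the comparison still matters.

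**What to change.** 1. Apply the same start-point rule, a common at-risk window that continues after PN weaning, and the same event definitions to both groups. State the control data source and calendar period.
2. Test between groups only events found from the same kind of records in both, such as culture-proven bloodstream infection. Include readmission only if readmissions elsewhere are captured equally, because the Treatment/Follow-up Period section returns patients to their referring physician.
3. Keep Fisher's test if every patient is fully observed over the window. Otherwise compare time to first event within it, by log-rank or a cause-specific Cox model, adjusting for the matching factors only where event numbers allow. Show cumulative incidence with death and transplant as competing events. Report exits by group and reason, since informative exit can still bias the result.
4. Report symptom-type and unequally monitored events for the Omegaven cohort with confidence intervals, and label any comparison with controls as descriptive.
5. Separately, reconcile the triglyceride monitoring frequency across the Abstract, the Treatment/Follow-up Period section, the Treatment Period and Extended Outpatient lists, and Monitoring and Possible Dose Reductions, so that it is clear what was looked for in the cohort.

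The cost is some SAP wording and the abstraction of start dates, exit dates and reasons, and defined events from control records. The loss is that events not recorded equally get no confirmatory P-value.
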